4.1 SCHEDULE OF PROCEDURES

Procedures/Assessments	Screening Visit	Visit 1 (Day 0 at Transplant)	Visit #2 (Day 7 post-transplant ± 2 days)	Visit #3 (Day 14 post-transplant ± 2 days)	Visit #4 (Day 21 post-transplant ± 2 days)	Visit #5 (at hospital discharge)	Visit #6 (Day 30 post-transplant ± 14 days)
Eligibility & Informed Consent	X						
Demographics/Characteristics	X						
Medical & Cardiac History	X						
Confirm Eligibility/Randomize		X					
Data Collection Donor Characteristics		X					
Patient Visit (recipient)	X	X	X	X	X	X	X
Tissue Collection for biopsy (donor heart prior to transport & prior to transplant)		X	X				
Mitochondrial Testing		X	X				
Data Collection Transplant Details		X					
Data Collection PGD Scores		X	X				X
Data Collection Inotrope Support		X	X			X	X
Right Heart Catheter Data		X					
Data Collection Mechanical Circulatory Support		X	X			X	X
Data Collection Invasive Ventilator Support		X	X				
Endomyocardial Biopsy (recipient)			X	X	X		X
Data Collection Patient Survival							X
Data Collection Graft Survival							X
Data Collection Post-Transplant Hemodynamics		X	X				X
Data Collection Immunosuppressive Meds & Induction (if applicable)		X	X			X	X
Data Collection ICU & Hospital Stay						X	
Data Collection Heart Graft-Related AEs and SAEs		X	X	X	X	X	X

5.0 DATA COLLECTION AND MANAGEMENT

5.1 DATA PROCUREMENT

Except for mitochondrial studies (research), all data collected will already exist in the medical record under standard of care. Tissue collected will undergo mitochondrial studies.

5.2 TIME PERIOD OF DATA UNDER REVIEW

- Data will be reviewed from the dates of 9/01/2021 to 8/31/2023. Data will be collected from the following timepoints: Post-heart transplant Day 0, Day 7, Day 14, Day 30 and at hospital discharge. Data will be collected prospectively and retrospectively.
- Information will be kept in REDCap for two years after the conclusion of the study.

5.3 VARIABLES COLLECTED

The following data points/variables will be collected:

- Incidence of primary graft dysfunction
- Initial use of mechanical circulator support: The use of ECMO, intra-aortic balloon, LVAD, RVAD or biVAD
- Number of inotropes/pressors at 24 hours post-transplant
- Inotropic support for first 72 hours: The following inotropic medication doses will be collected at ICU admission T0, T12, T24, T48, and T72 hours after ICU admission post-heart transplantation:
 - Dopamine – mcg/kg/min
 - Dobutamine – mcg/kg/min
 - Amrinone – mcg/kg/min
 - Milrinone – mcg/kg/min
 - Epinephrine – mcg/kg/min
 - Norepinephrine – mcg/kg/min
- Initial use of mechanical respiratory support: Duration of initial post-transplant invasive ventilator support from time of initial admission to ICU post heart transplant until extubation
- Immunosuppression Medications (at day 7 and at time of discharge)
- Incidence of reperfusion injury on endomyocardial biopsy
- Cardiac index
- Cardiac output
- Blood pressure
- Mean arterial pressure
- Pulmonary artery pressure
- Pulmonary capillary wedge pressure
- Left atrial pressure
- Right atrial pressure
- Right ventricular pressure
- Stroke volume
- Ejection fraction
- BUN and Creatinine
- Liver function tests

- Cellular rejection
- Antibody mediated rejection
- Graft-related serious adverse events
- Mitochondrial function
- Age at transplant
- Sex
- Donor characteristics
- Total cross clamp duration in minutes
- Ischemic time
- Surgical complications
- Total length of stay
- ICU length of stay
- Total blood products used
- Trans-thoracic echocardiogram results prior to discharge:
 - Ejection Fraction (EF%)
 - Wall motion assessment
 - LV Septal and posterior wall thickness
 - Any valve abnormalities
- Patient and graft survival at day 30
- Incidence of acute cellular rejection in the first 30 days post heart transplant
- Incidence of antibody mediated rejection in the first 30 days post heart transplant
- Adverse events: All heart graft-related serious adverse events and any heart graft-related adverse events will be followed and documented until the investigator designates the event to be either resolved or its effect on the patient's condition stabilized.
- Medications: Medications used to treat all serious heart graft-related adverse events (SAEs) until the SAE is resolved.

5.4 SOURCE DOCUMENTS

- Source documents are defined as the results of original observations and activities of a clinical investigation. Source documents will include, but are not limited to, progress notes, electronic data, computer printouts, screening logs, and recorded data from automated instruments. All source documents pertaining to this trial will be maintained by the investigators and made available for inspection by authorized persons.

5.5 DATA COLLECTION AND STORAGE

- During each subject assessment, an investigator participating in the trial will record progress notes to document all significant observations. In addition, any contact with the subject via telephone or other means that provides significant clinical information will also be documented in the progress notes.
- All data required by the trial protocol will be completely and accurately entered into the REDCap database by the investigator or his or her designate, identifying subjects

by subject number.

- Essential trial documents must be maintained by the Investigator for at least 7 years.
- **Storage of Physical Records:** Physical records will be maintained for this study at a secure location where access is limited to approved personnel. The records will not be removed from Cedars-Sinai premises.
- **Storage of Specimens:** Specimens will be maintained for this study at a secure location where access is limited to approved personnel. The specimens will not be removed from Cedars-Sinai premises.

5.6 CONFIDENTIALITY AND SECURITY OF DATA

- **Secure storage:** Data will be housed in a HIPAA-compliant secure storage system, like REDCap or Box, within the Cedars-Sinai network with access restricted to approved members of the research team.
- **Limited Access:** Private identifiable information, will be accessible only to IRB approved study team members with current IRB training.
- **Unique ID Numbers:** Each patient will be assigned a unique ID number, which will be used to code data and specimens.

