2.0 STUDY OBJECTIVES

Primary Objective

To compare the SherpaPak™ Cardiac Transport System to standard of care cold storage of donor hearts for transplantation.

Secondary Objective

To assess for a decrease in cold injury of donor hearts and therefore a decrease in primary graft dysfunction. To assess for events between study groups.

Primary Endpoint

The primary endpoint will be a composite endpoint of: Absence of moderate to severe primary graft dysfunction per ISHLT grading scale (left or right ventricle) in the first 24 hours post transplantation, and 30-day patient survival, 30-day incidence of ischemic reperfusion injury on endomyocardial biopsies and changes in mitochondria function and quality (at donor heart harvesting, at the time just prior to donor heart implantation and at one-week post- heart transplantation).

Secondary Endpoints – To describe between the groups

1. Each individual component of the composite endpoint will be assessed.
2. Hemodynamic parameters including cardiac index, cardiac output, blood pressure, mean arterial pressure, pulmonary artery pressure, left atrial pressure, right atrial pressure, right

ventricular pressure, stroke volume and ejection fraction at 24 hours post-transplant

3. The number of inotropes/pressors at 24 hours post -transplant.
4. Incidence of acute cellular rejection in the first 30 days post heart transplantation.
5. Incidence of antibody mediated rejection in the first 30 days post heart transplantation.
6. Incidence of heart graft related Serious Adverse Events in the first 30 days post heart transplantation.
7. Total length of stay
8. ICU length of stay
9. Number of blood products used

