3.4 SUBJECT SCREENING AND ENROLLMENT

All patients on the heart transplant waiting list at Cedars-Sinai will be identified by trial investigators and screened for trial eligibility. Those patients who initially appear eligible for the trial will have the trial thoroughly explained to them by a trial investigator, be invited to participate, and will be asked to sign an informed consent. Consent of a legally authorized representative of a cognitively impaired individual will be obtained before the cognitively impaired individual may be included in research.

When a matching donor heart becomes available, the inclusion and exclusion criteria will be re-verified by the study team. If the recipient is no longer eligible for the trial, they will be considered a screen failure and they will exit the study and no information will be collected for these patients.

If the subject is matched with a donor heart from a local donor (Southern California), the

subject will be considered a screen failure and they will exit the study and no information will be collected for these patients.

When a matching donor heart from a non-local donor offer (from Northern California, Arizona, Nevada or farther geographies) becomes available the recipient will be assigned a subject identification number and randomized 1:1 to receive a heart transported using either standard of care cold storage or the SherpaPak™ Cardiac Transport System. REDCap will be used for randomization.

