4.0 STUDY DESIGN AND METHODS

This study is designed to be conducted as a single-center randomized prospective trial to compare the SherpaPak™ Cardiac Transport System to standard of care cold storage for donor hearts in transplantation. Approximately 20 consented subjects will receive a donor heart transported using either cold storage or the SherpaPak™ Cardiac Transport System, respectively. Both methods are FDA approved.

Donor hearts will be screened for eligibility based on current standard of care criteria. Heart transplant candidates will be screened for trial eligibility. Every eligible candidate will be asked to participate. Eligible and consented transplant candidates will receive donor hearts transported using standard of care cold storage or the SherpaPak™ Cardiac Transport System, that have been deemed clinically acceptable for transplantation by the treating transplant clinical team.

The study will be evaluating the comparative use of two FDA-approved methods for organ procurement. The research procedures will be randomization, data collection/analysis, and tissue collection from standard of care biopsies for mitochondrial testing.

Mitochondrial Testing

Biopsy tissue from donor hearts will be collected prior to transport, prior to transplant and at one-week post-transplant. The tissue will be evaluated to detect changes in mitochondrial function and regulation.

Biopsy tissue will be processed and stored by the [name] Laboratory at Cedars-Sinai. The [name] Laboratory, led by [name], is studying the molecular mechanisms regulating mitochondria in the heart's response to ischemic injury.

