6.0 DATA AND SAFETY MONITORING

6.1 DATA AND SAFETY MONITORING PLAN

Safety will be analyzed principally by examination of the frequency of adverse events. In particular, the number of donor heart graft-related serious adverse events (SAEs) up to the 30-day follow-up after transplantation per subject will be analyzed. This endpoint is defined to consist of the following adverse events (at most one per type), if they are serious adverse events:

- Primary heart graft dysfunction (not including rejection or cardiac tamponade):
 - Use of ECMO, RVAD, LVAD, BiVAD or insertion of a new IABP for >12 hours post TX.
 - Use of ≥ 2 inotropic agents/vasopressors including high-dose epinephrine or norepinephrine for >7 days post heart TX.
 - Open chest post heart TX. due to compromised heart function
- Primary graft failure requiring re-transplantation

Subjects will be monitored before, during and after the operative procedure to help ensure their safety. The investigators are members of transplant teams who have extensive experience with heart transplants and who will be trained to use the SherpaPak Cardiac Transport System to further minimize risk.

Subjects in the trial will undergo frequent visits and routine monitoring to help detect any abnormal changes and to provide appropriate treatment as necessary.

An independent Data and Safety Monitoring Board (DSMB) comprised of two expert heart failure physicians and one cardiothoracic surgeon not participating in the trial, will perform

monitoring activities to ensure the identification, documentation, and analysis of adverse events; and to ensure compliance with the protocol and procedures that are in place for conducting research to protect the safety and well-being of all subjects. The DSMB will have a formal meeting at least once annually. Frequency of the meetings may be changed by the DSMB in consultation with the Principal Investigator based on need. An ad hoc meeting may be called at any time by the Chairperson or by the PI and research staff should ethical or patient safety issues arise.

A status update will also be provided to the DSMB on a quarterly basis via email correspondence by the DSMB Coordinator.

The criteria below provide guidance for suspending trial enrollment/randomization until review by the DSMB. Selected serious adverse events (SAEs) of concern and their thresholds are:

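### The protocol does not say whether the PGD grader, the biopsy reader or the mitochondrial laboratory is masked to the transport method, and low-cost steps could limit the resulting bias

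*Combined protocol and SAP*

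**What the plan says.** Section 4.0 describes a "single-center randomized prospective trial". Under Section 3.4, once a non-local donor heart is available, the recipient receives a subject number and is "randomized 1:1 to receive a heart transported using either standard of care cold storage or the SherpaPak™ Cardiac Transport System", through REDCap.

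The primary endpoint in Section 2.0 has four components. The first is "Absence of moderate to severe primary graft dysfunction per ISHLT grading scale (left or right ventricle) in the first 24 hours post transplantation". The others are "30-day patient survival, 30-day incidence of ischemic reperfusion injury on endomyocardial biopsies and changes in mitochondria function and quality".

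On the people involved, Section 6.1 states: "The investigators are members of transplant teams who have extensive experience with heart transplants and who will be trained to use the SherpaPak" system. Section 3.5 adds that all subjects are patients of the principal investigator and co-investigators. Under Section 5.5 the trial data are "entered into the REDCap database by the investigator or his or her designate". Section 5.1 says that everything except the mitochondrial studies comes from the routine medical record.

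The only provision resembling concealment is in Section 5.6: "Each patient will be assigned a unique ID number, which will be used to code data and specimens". It stands beside secure storage and restricted access, under confidentiality.

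**The concern.** An ID code protects the patient's identity. It hides the arm only from someone who cannot link the code to the allocation, and no section says that any assessor is in that position. Section 3.4 issues the subject number at the same step as randomization, and REDCap serves for both randomization and data entry. Section 5.6 limits access to approved team members but hides allocation from none of them.

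Followed as written, the protocol therefore allows PGD and biopsy reperfusion injury to be scored by people who know how the heart was transported. If that knowledge shifts borderline calls, the shift goes straight into the primary endpoint. Section 7 plans descriptive summaries only, so nothing later in the plan would detect or correct it. A proof-of-concept signal is the study's main product, and describing a biased difference instead of testing it does not make it less biased.

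**Working it through.** The plan states no error rate, power, event rate or effect size, so there is no figure of its own to reproduce. The check is textual, followed by simple arithmetic.

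**Step 1: is masking mentioned?** Sections 1.0 to 7.2 contain no statement on masking, blinding, open-label conduct or endpoint adjudication. The DSMB in Section 6.1 has a safety and compliance remit and is not described as an endpoint committee.

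**Step 2: which primary components depend on a grade or reading?**
- PGD: a grade on the ISHLT scale. Section 4.1 lists PGD scores as a collected item. The grader is not named and no derivation rule is given.
- Reperfusion injury on biopsy: a reading. The reader is not named.
- 30-day survival: neither a grade nor a reading.
- Mitochondrial function and quality: Section 4.0 names the purpose and an in-house laboratory but describes no assay. Subjectivity is possible but not shown.

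The count is at least two of four.

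**Step 3: who knows the arm?** Sections 3.5, 5.5 and 6.1 together make the investigators treating clinicians, trained on the device, who supply the data. Section 6.1 also has them judge whether adverse events relate to the preservation method, which requires knowing it. For the biopsy reader and the laboratory the documents are silent.

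**Step 4: what does one regraded subject do?** Section 4.0 gives the size as "Approximately 20 consented subjects will receive a donor heart transported using either cold storage or the SherpaPak™ Cardiac Transport System, respectively". With 1:1 allocation this could mean 10 or 20 per arm, so both are shown. The shift in an arm's rate is 1/n:
- n = 10: 1/10 = 10 percentage points. For example, 3/10 in both arms becomes 2/10 against 3/10.
- n = 20: 1/20 = 5 percentage points.

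**Step 5: illustration under assumed inputs.** Let p be an event rate equal in both arms, and m the share of device-arm events that a grader who knows the arm scores down. Both are assumptions, as is the direction. The expected spurious difference is p × m, and the chance of at least one regraded subject is 1 − (1 − p × m)^n.

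| p | m | p × m | chance, n = 10 | chance, n = 20 |
|---|---|---|---|---|
| 0.10 | 0.10 | 1 point | 9.6% | 18.2% |
| 0.30 | 0.25 | 7.5 points | 54.1% | 79.0% |
| 0.50 | 0.50 | 25 points | 94.4% | 99.7% |

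For the middle row, 1 − 0.925^10 = 0.541 and 1 − 0.925^20 = 0.790. The outer rows bound the range examined, with p and m each from 0.10 to 0.50. This arithmetic applies to the two yes/no components, not to a continuous mitochondrial measure.

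**The case against.** A reader might infer that this is an open-label trial with unmasked assessors. The documents do not say so; they are silent. Nothing shows that the biopsy reader or the laboratory learns the arm. The supportable statement is that masking is not specified.

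A reader might also count three judged components. Without a described assay, only two are shown.

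The strongest argument concerns PGD. If the grade can be computed from recorded values, there is little room for a lenient call; if it cannot, a derivation rule will not work. This stands in part. The protocol provides for no such computation, so the room exists as written. However, the ISHLT criteria are not reproduced in the documents, so the sponsor must confirm that the collected values are sufficient. A rule also leaves one route of bias open: a team that knows the arm decides on devices and inotropes, and those decisions feed the grade.

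Two practical objections also stand. Section 6.1 requires severe PGD with mechanical support in SherpaPak subjects to reach the DSMB within 24 hours, so a prompt grade with the arm known must remain. The biopsies are standard of care and nothing says that clinical pathology uses the study code, so rerouting specimens or adding a masked re-read cannot be called almost free.

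Finally, a 1/n shift is a property of any yes/no outcome and is not evidence that bias will occur. The study is an internally funded descriptive pilot with no test or decision threshold to distort. That limits the consequence but does not remove it.

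**Conclusion.** The point holds as an unspecified safeguard. The protocol does not provide for masking of the PGD grader, the biopsy reader or the mitochondrial laboratory; the investigators in practice know the transport method and enter the data; and the ID code is only a confidentiality measure. At least two of the four primary components are exposed.

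The sensitivity is 10 points per regraded subject at 10 per arm, or 5 points at 20 per arm, depending on how the sample size is read. Whether any regrading would occur, how often and in which direction are assumptions. The documents do not support saying that assessors are known to be unmasked, or that results would favor the device. The change is worth making because part of the exposure can be removed at low cost. The gap does not invalidate a descriptive pilot.

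**What to change.** 1. **Mitochondrial laboratory.** State in Sections 4.0 and 5.6 that the laboratory receives tissue under a code it cannot link to allocation, and that allocation is hidden from it in REDCap until its results are locked.
2. **Biopsy reading.** Leave the transport arm off any research information sent with recipient biopsy requests. Keep the routine clinical pathology pathway and add no second reader.
3. **PGD.** Derive the endpoint grade by a written rule that applies the ISHLT scale to values already listed in Section 5.3 (support devices, inotrope doses, hemodynamics, ejection fraction), run on a dataset without the arm variable. Confirm that these values are sufficient and say which recorded times count toward the first 24 hours, since Section 5.3 times the doses from ICU admission. State that this grade is the one used for the primary endpoint. The unmasked clinical grade continues to serve DSMB reporting under Section 6.1.

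The cost is protocol wording, a REDCap access setting and a little extra data handling, with two PGD grades on file. Masking will be imperfect where the chart names the device, and bias from support decisions made by a team that knows the arm will remain. The report should acknowledge both limits.

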6.0 DATA AND SAFETY MONITORING

6.1 DATA AND SAFETY MONITORING PLAN

Safety will be analyzed principally by examination of the frequency of adverse events. In particular, the number of donor heart graft-related serious adverse events (SAEs) up to the 30-day follow-up after transplantation per subject will be analyzed. This endpoint is defined to consist of the following adverse events (at most one per type), if they are serious adverse events:

- Primary heart graft dysfunction (not including rejection or cardiac tamponade):
 - Use of ECMO, RVAD, LVAD, BiVAD or insertion of a new IABP for >12 hours post TX.
 - Use of ≥ 2 inotropic agents/vasopressors including high-dose epinephrine or norepinephrine for >7 days post heart TX.
 - Open chest post heart TX. due to compromised heart function
- Primary graft failure requiring re-transplantation

Subjects will be monitored before, during and after the operative procedure to help ensure their safety. The investigators are members of transplant teams who have extensive experience with heart transplants and who will be trained to use the SherpaPak Cardiac Transport System to further minimize risk.

Subjects in the trial will undergo frequent visits and routine monitoring to help detect any abnormal changes and to provide appropriate treatment as necessary.

An independent Data and Safety Monitoring Board (DSMB) comprised of two expert heart failure physicians and one cardiothoracic surgeon not participating in the trial, will perform

monitoring activities to ensure the identification, documentation, and analysis of adverse events; and to ensure compliance with the protocol and procedures that are in place for conducting research to protect the safety and well-being of all subjects. The DSMB will have a formal meeting at least once annually. Frequency of the meetings may be changed by the DSMB in consultation with the Principal Investigator based on need. An ad hoc meeting may be called at any time by the Chairperson or by the PI and research staff should ethical or patient safety issues arise.

A status update will also be provided to the DSMB on a quarterly basis via email correspondence by the DSMB Coordinator.

The criteria below provide guidance for suspending trial enrollment/randomization until review by the DSMB. Selected serious adverse events (SAEs) of concern and their thresholds are:

- Two (2) episodes of severe primary graft dysfunction (PGD) per ISHLT grading criteria (left or right ventricle, not including rejection or cardiac tamponade) requiring use of a mechanical circulatory support (MCS) device within 24 hours after transplant in subjects randomized to the SherpaPak method of transport.
- Two (2) deaths occur in subjects randomized to the SherpaPak method of transport within 7 days after transplant.

It is the responsibility of the Principal Investigator to report all of the above SAEs to the DSMB within 24 hours of discovering the event.

In the event that the study is suspended, no new subjects will be consented or randomized to the trial. Subjects already in follow-up on the study will continue to be followed as outlined in the protocol unless the appointed Chair provides further recommendations.

All heart graft-related adverse events and serious adverse events are to be recorded on the electronic case report forms until post-transplant day 30. The description of the adverse event will include: the date of onset, duration, severity, seriousness, the relationship of the event to the trial treatment, anticipated or not, and any treatment required. All serious adverse events occurring during the course of the first 30 days post-transplant will be documented on the appropriate electronic case report form(s) in REDCap. Heart graft-related AEs will be recorded up to the 30-day follow-up or through hospital discharge if longer than 30 days. The principal investigator is responsible for the classification and reporting of heart graft-related adverse events to the appropriate regulatory authorities.

A SAE is any AE that in the view of the Investigator results in death, is life-threatening, requires inpatient hospitalization or causes prolongation of existing hospitalization. In the interest of patient safety, and in order to fulfill regulatory requirements, all SAEs (regardless of their relationship to the study procedures) will be documented and reported per IRB guidelines. In the interest of this study, the SAEs that meet the stopping rule criteria within the DSMB Charter, will be submitted to the DSMB for review.

Heart-graft related-AEs will be captured in this study. The investigator will assess the relationship of the AE to the SherpaPak Cardiac Transport System or to the standard of care methods of preservation. The relationship will be assessed using the following categories:

- Definitely Related: There is a reasonable causal and temporal relationship between preservation with the SherpaPak Cardiac Transport System and the adverse event.
- Probably Related: It is more likely than not that there is a reasonable causal relationship between preservation with the SherpaPak Cardiac Transport System and the adverse event.
- Possibly Related: There is a reasonable relationship with preservation with the SherpaPak Cardiac Transport System and the adverse event, but the causal relationship is unclear or lacking.
- Unlikely Related: There is a temporal relationship with preservation with the SherpaPak Cardiac Transport System and the adverse event, but there is not a reasonable causal relationship between the trial device and the event.
- Unrelated: There is no relationship between preservation with the SherpaPak Cardiac Transport System and the adverse event.

The investigator will rate the severity of the adverse event using the following categories:

- Mild: The adverse event is transient and/or easily tolerated by the subject.
- Moderate: The adverse event causes the subject discomfort and interrupts the subject's usual activities.
- Severe: The adverse event causes considerable interference with the subject's usual activities.

During the trial, investigators will be responsible for complete and accurate entry of data into the trial's REDCap database, and will maintain on file the following accurate, complete and current records relating to this trial:

- All relevant correspondences and required reports that pertain to the trial
- Records of receipt, use or disposition of the investigational device, including the type and quantity of the device; the dates of receipt; the lot number; the names of all persons who received, used or disposed of each device; and why and how any units of the device have been returned to the Sponsor, repaired, or otherwise disposed
- Records of each subject's case history and exposure to the device
- Signed and dated consent forms
- Protocol, and any amendments
- Investigator curriculum vitae

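### The per-subject count of graft-related SAEs omits death from graft failure and relies on duration thresholds, so some graft deaths score 0 while survivors on longer support score 1

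*Combined protocol and SAP*

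**What the plan says.** Section 6.1 (Data and Safety Monitoring Plan) says that safety rests mainly on the frequency of adverse events, and then singles out one measure: "the number of donor heart graft-related serious adverse events (SAEs) up to the 30-day follow-up after transplantation per subject will be analyzed". It defines that measure by a list: "This endpoint is defined to consist of the following adverse events (at most one per type), if they are serious adverse events".

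The list has two main entries. The first is primary graft dysfunction, excluding rejection and tamponade, with three criteria:

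- The first concerns mechanical support and carries a threshold in hours: "Use of ECMO, RVAD, LVAD, BiVAD or insertion of a new IABP for >12 hours post TX".
- The second concerns drug support and carries a threshold in days: "Use of ≥ 2 inotropic agents/vasopressors including high-dose epinephrine or norepinephrine for >7 days post heart TX".
- The third is a chest left open because the heart is functioning poorly, with no threshold of time.

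The second is graft failure that leads to re-transplantation. Death is not an entry, and no rule covers a subject who dies before reaching a duration threshold.

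Later in section 6.1, death appears as one of the conditions that make an event serious: "A SAE is any AE that in the view of the Investigator results in death". Section 2.0 lists, as secondary endpoint 6, "Incidence of heart graft related Serious Adverse Events in the first 30 days post heart transplantation", without referring to the list in section 6.1.

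**The concern.** A count of graft-related serious events should not fall because a subject died sooner. Here it can. The inotrope criterion needs more than 7 days of support. The mechanical-support criterion needs more than 12 hours, at least for a new IABP and possibly for every device named. Graft failure counts only through re-transplantation, which a subject who dies first does not receive.

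Section 7.2 plans mainly descriptive comparisons, so no model or test stands between the raw counts and the reader. If early graft deaths were unequal between arms, this count could favour the arm with more of them.

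**Working it through.** The plan gives no event rate, power or target for this count, so there is no figure to reproduce. The check applies the section 6.1 list as a scoring rule to hypothetical subjects.

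**Inputs**

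- The list, its cap of one per type and its seriousness filter: section 6.1.
- Size: about 20 subjects (section 4.0), which could be a total or a number per arm. Allocation is 1:1 (section 3.4). Both 10 and 20 per arm are used.
- Reading A: the 12-hour threshold applies to every device. Reading B: it applies only to a new IABP.
- A type is either one of the 2 main entries or one of the 4 separate criteria (three for dysfunction plus re-transplantation).
- Assumption: every listed event is judged serious.

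**Scores**

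| Hypothetical subject | Reading A | Reading B | With graft death added as a type (A; B) |
|---|---|---|---|
| Early graft death, no device, closed chest | 0 | 0 | 1; 1 |
| Graft death at hour 10 on new IABP, closed chest | 0 | 0 | 1; 1 |
| Graft death Day 5 on at least 2 agents, no device, closed chest | 0 | 0 | 1; 1 |
| Graft death at hour 10 on ECMO, closed chest | 0 | 1 | 1; 2 |
| Graft death at hour 10 on ECMO, open chest | 1 | 1 (2 types) or 2 (4 types) | 2; 2 or 3 |
| Graft death Day 3 after 72 h of ECMO, closed chest | 1 | 1 | 2; 2 |
| Survivor, at least 2 agents for 8 days, no device, closed chest | 1 | 1 | 1; 1 |
| Survivor, new IABP for 13 h | 1 | 1 | 1; 1 |

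The first three profiles score 0 under both readings and both meanings of type. The hour-10 ECMO death with a closed chest scores 0 only under reading A. Open chest has no duration threshold, so an early death with the chest open for compromised function scores at least 1.

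**Effect on an arm**

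- One unscored death, compared with scoring it 1, lowers the arm's mean count by 1/10 = 0.10 (10 per arm) or 1/20 = 0.05 (20 per arm).
- Illustration: one arm has two graft deaths before Day 7 with no device and closed chest; the other has two survivors with 8 days of qualifying support. With 10 per arm the count reads 0/10 against 2/10, a gap of 20 percentage points in favour of the arm with the deaths. With 20 per arm it is 0/20 against 2/20, a gap of 10 points. If there are no other deaths, 30-day survival reads 8/10 against 10/10, or 18/20 against 20/20.

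**How often it could arise**

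The documents give no rate. For an assumed early graft-death risk p, the chance of at least one such death in an arm of n is 1 − (1 − p)^n:

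- n = 10: 1 − 0.97^10 = 26% at p = 3%; 1 − 0.90^10 = 65% at p = 10%.
- n = 20: 1 − 0.97^20 = 46% at p = 3%; 1 − 0.90^20 = 88% at p = 10%.

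These are upper limits for the problem at each assumed risk, because not every such death would score 0.

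**The case against.** The strongest reply is that deaths are handled elsewhere. Thirty-day survival is part of the primary composite, and secondary endpoint 1 assesses each component separately (section 2.0). Moderate to severe graft dysfunction in the first 24 hours, by ISHLT grade, is in the same composite, and the section 6.1 durations are not stated there. Patient and graft survival at day 30 are collected (sections 4.1 and 5.3). All SAEs in the first 30 days are documented, and two deaths within 7 days in the SherpaPak arm are a criterion for suspending enrolment pending DSMB review (section 6.1). Keeping mortality in survival and morbidity in an event count is a recognised way to avoid counting a death twice. This stands, and it limits the consequence: a reader who sees 8/10 against 10/10 alive will not think the first arm safer. It does not repair the count, which is to be analysed in its own right.

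A second reply is that a fatal event is serious by definition and so must count. It does not follow. Seriousness filters the listed events; it does not add an event to the list.

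A third is that the three dysfunction criteria may be examples only. The wording that introduces the list does not read that way. If it was meant so, assessors have no rule for scoring a death that meets none of them.

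A reader might also infer that this count is the principal safety analysis. Section 6.1 does not say so: the word describing the main approach attaches to adverse-event frequency in general, and the graft-related count follows as a particular case.

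**Conclusion.** The point holds in a limited form. Followed exactly, the section 6.1 list gives some graft deaths a lower score than some recoveries, and three of the fatal profiles above score 0 under every combination tested. The conclusion rests on taking the list as closed, as its wording indicates.

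Three stronger inferences are not supported:

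- That early graft deaths generally score 0. Open chest, longer device support and, under reading B, any ECMO or VAD use still count.
- That secondary endpoint 6 shares the defect. It does not cite the list, and section 5.3 speaks of all graft-related serious events, so a fatal graft event could count there.
- That the trial would lose deaths or reach a wrong overall safety conclusion. The deaths are visible elsewhere, and no test, margin or decision rule uses this count.

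The 20-point and 10-point gaps depend on an assumed split of two deaths against two survivors, and the 26% to 88% range on assumed risks. The change is worth making because the rule is stated, its result is perverse and the correction is small.

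**What to change.** In section 6.1, add death attributed to graft failure or dysfunction within 30 days as one listed event type, counted once per fatal episode. Do not also waive the duration thresholds for subjects who die: with type undefined, one fatal episode could then score both as a death and as a support criterion it never met. Every graft death in the table then scores at least 1, and survivor scores do not change.

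Take attribution from the investigator's SAE record plus one cause-of-death field. The field is needed because section 5.3 lists survival but not cause of death, and the relationship categories in section 6.1 concern the preservation method, not whether the graft failed.

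State that secondary endpoint 6 uses the same definition. State which devices the 12-hour threshold covers, and whether a type is a main entry or a single criterion. These are scoring clarifications and leave patient care unchanged.

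The cost is a wording amendment, one added data field, slightly higher event counts, and an overlap with 30-day survival that the report should mention.
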